## Blood, CSF, and Tissue Biomarker Methods

**Blood Collection Procedures/Measures:** Participants will fast overnight prior to blood draw before 10 a.m. Whole blood will be collected and processed as described.  Fasting blood for neuroendocrine measures will be collected multiple times during the study period (visits 1, 3, 6-13). The total volume of blood to be collected for neuroendocrine measures of stored blood ranges from 40-70mL (about 3-5 tablespoons) at cognitive Pre/Post Diet and Follow-up visits, and 25mL (about 2 tablespoons) at the lumbar puncture visits. Included in this amount is blood to be stored for use in future studies. Participants will sign a repository-consent for storage of samples at time of study consent. Additionally, 8.5mL of blood will be collected during the first week and again at 12 weeks for safety labs and measurement of metabolic outcomes. The total amount of blood to be collected in this study will not exceed 400mL over the 24-week study.

Samples will be immediately placed on ice and spun within 30 minutes at 2200 rpm in a cold centrifuge for 15 minutes. Plasma, serum, and red blood cells will be aliquoted into separate storage tubes and flash frozen at -80°C until assays are analyzed. The following assays will be performed.

## Metabolic assays:

Metabolic measures will be assessed at the Pre-Diet, Mid-Diet and Post-Diet visits. These will include, glucose, insulin, lipids (HDL, LDL, VLDL, and triglycerides) will be measured by LabCorp diagnostics.

# **APOE** genotyping:

Additional blood (up to 10 ml, Visit 2) will be drawn for confirmation and validation of ApoE genotyping by the Laboratory of [name] at Wake Forest School of Medicine. Participants that have already had APOE genotyping done as a part of another ADCC stuidy will not have to repeat this procedure. The total amount of blood to be drawn at this visit, including blood for the repository, mitochondrial assay and genotyping, is 70 ml (~5 tablespoons).

# Mitochondrial respiration assays:

To determine bioenergetic profiles of intact cells, we will assess basal respiration (Basal-OCR), maximal respiration (MAX), ATP coupled respiration (ATP-OCR), proton leak (Leak), and non-mitochondrial respiration (non-mito). The spare respiratory capacity (SRC) will be calculated by subtracting Basal-OCR from MAX. A Seahorse XF96e will be used to run samples in triplicate. Basal-OCR measurements will be performed with standard fuel conditions designed to examine glucose oxidation (pyruvate and glucose). Oligomycin will be added to block ATP synthase. The resultant decrease in oxygen consumption (ATP-OCR) reflects the amount of oxygen consumed to fuel the conversion of ADP to ATP. FCCP will be added to uncouple mitochondria and induce maximal oxygen consumption. The resultant increase in oxygen consumption represents MAX. Antimycin-A and rotenone will be added to block electron transport chain activity. Residual respiration is non-mitochondrial. Oxygen consumption not linked to ATP synthesis (Leak) will be measured by subtracting non-mito OCR from the rate left after the blockage of ATP synthase by oligomycin.

## Epigenomics/Transcriptomics

Read Mapping/Counting: Illumina sequencing runs will be processed to generate FastQ files using the Illumina provided configureBclToFastq.pl script to automate running CASAVA, using default parameters for removal of sequencing reads failing the chastity filter and mismatches in the barcode read. Reads will be trimmed for QC using *Btrim* (5 base sliding window average with Q > 15) and to remove any adaptor sequence using ea-utils. The current Ensembl Homo Sapiens reference file, annotations and Bowtie2 indexes will be used for mapping of the sequencing reads to the genome and read counting. Bowtie2 and TopHat2 will be used to map the sequencing reads to the genome using a mate-innerdistance of 100 bp and 'firststrand' options. 74,75 Following alignment, read counts per gene will be obtained using HTSeg(88).Pre-Processing and QC of mRNA Raw Count Data will be performed in R using Bioconductor packages. Counts will be converted to Counts Per Million (CPM) using the cpm function of the edgeR package,  and all features with CPM ≤ 0.25 in ≥90% will be removed. We will use the biomaRt package and the Ensembl BioMart database to obtain Entrez Gene IDs. Gene Symbols, genome coordinates, gene length and percent GC content for detectable features. We will perform differential isoform expression analysis.  To use linear modeling in *R*, we will transform the raw count data to log CPM,78 and use the Trimmed Mean of M-values (TMM) normalization method79 implemented in the calcNormFactors function in the edgeR Bioconductor package.80 We will adjust for flow cell effects. Pre-Processing and QC of DNA Methylation Data: The raw DNA methylation microarray data will be pre-processed with published pipelines for expression and methylation implemented in R using Bioconductor packages. The final methylation value for each probe is computed as the M-value (log ratio of methylated to unmethylated intensity). 81 Filters applied to the probes for the CpG sites include detected methylation levels in <90% of the samples using a p-value of

0.05, 65 probes that assay highly polymorphic single-nucleotide polymorphisms (SNPs) rather than CpG sites, and overlap with a repetitive region. We will flag probes containing any SNPs within 10 base pairs of the targeted CpG site.

## Neural-Derived Exosome Markers of Insulin Resistance

Exosome isolation and L1 CAM enrichment methods have been described. 35, 82, 83 Plasma will be mixed with Thromboplastin-D followed by ExoQuick precipitation solution (System Biosci). Exosome suspensions will be incubated, centrifuged, re-suspended with protease and phosphatase inhibitors inhibitor cocktails and immunoprecipitated using mouse anti-human CD171 (L1 CAM) biotinylated antibody (eBiosci). After pellet re-suspension and biotin elution, exosomes will be lysed. To quantify p-panTyr-IRS-1, we will use MesoScale Discovery plates for IRS-1 with Anti-Phospho-Tyr Antibody Sulfo-TAG Labeled detection antibody, and for Ser312-IRS-1, Phospho-IRS-1 (Ser312) Kit. To normalize, we will use measurements of exosome marker human CD81 (Hölzel Diagnostika-Cusabio), with verification of the CD81 antigen standard curve using human purified recombinant CD81 antigen (Origene). The mean value for CD81 in each assay group will be set at 1.00 and the relative values for individual samples will be used to normalize their recovery. The insulin resistance index R will be the target outcome.

**Nutritional Data Information:** Nutritional data for this study will be collected by two methods. First, participants will complete food diaries. These will be completed at least 3 times per week during the first week on a diet and once a week thereafter. Food/drink description, amount (in ounces), time consumed will be recorded. Second, 24-Hour food recalls will be utilized at several points throughout the study (pre and post both diets). The ASA24 (Automated Self-Administered 24-hour Recall) system from the National Cancer Institute will be used for data collection. Participants will complete these 24-hour recalls with help from the study dietitian, or other study staff, and may complete the recalls themselves once they receive training on how to use the ASA24 program. Similar information to the food diaries will be recorded with the 24-hour recalls (food/drink description, amount (in ounces), time consumed).

## STATISTICAL CONSIDERATIONS

## Statistical Analysis and Power

Statistical analyses will be overseen by [name], Wake Forest ADCC Data Core member, who has extensive experience in the analyses of clinical trials and in using results from Phase II studies to design efficient Phase III trials. We will examine change in our primary outcome CSF AB42, using analysis of covariance to compare mean levels at 4-months between intervention groups with adjustment for baseline level, age, and MMSE. Two-sided type 1 error for the primary outcome will be controlled at 0.05 and the primary analysis (intention to treat) will include all data on participants grouped according to intervention assignment, regardless of adherence. If residuals from this model are markedly skewed, we will perform supporting analyses after data transformation. Similar approaches will be used for other secondary outcomes of our primary aim (e.g. PET, MRI, CSF). Mixed effect models will be used for repeated measures (cognition). To examine whether any differences in these outcomes are moderated by APOE genotype, amyloid PET positivity, insulin resistance (secondary aims), or by gender, we will use tests of their interaction with intervention assignment. Additional aims involve examining how changes among outcomes differ between intervention groups and whether they track with markers of hypothesized mechanisms. We will explore the intercorrelations among changes using multivariate decomposition and assess whether these differ between intervention groups. We will also assess mediation, using models in Emsley et al. 2010^84 to identify potential underlying mechanisms.

**Power Analysis for Primary Endpoints:** Sample size estimates for the proposed study were based on the results of our small pilot study showing 6-week mean MMKD vs AHAD diet changes in CSF

Aβ42 of 89 vs 11 units (pooled SD of changes 102). With 2-sided type 1 error of 0.05, if attrition is as large as 15% (our observed pilot attrition was 10%), and allowing a 10% attenuation of effect related to possible non-adherence, enrolling 53 participants/group provides >90% power: thus, we target N=60/group. The proposed longer 4-month intervention and covariate adjustment may increase power to detect a true difference.

**Power analyses for Secondary and Exploratory Endpoints:** The exploratory nature of these aims in this Phase II trial are necessary to identify potential outcomes, biomarkers and therapeutic targets for follow-up and confirmation in future trials; thus we have not applied formal power analyses to these aims. However, we note that enrolling N=60 per group provides 80% power to detect mean differences (t-tests) of 0.56 SD in other outcomes.

## **ASSESSMENT OF SAFETY**

**Safety and Compliance Monitoring**. All participants will be medically supervised by Co-investigator [name]. Safety monitoring will be overseen by a Data and Safety Monitoring Board approved by the study sponsor, the National Institute on Aging, as detailed in Protection of Human Subjects. Compliance will be assessed by regular capillary ketone measurement and dietitian-rated compliance based on food records. In our 4-month pilot study, mean compliance rates were 4.5 and 4.75 out of 5 (perfect compliance) for the MMKD and AHAD diets

# Data and Safety Monitoring

The principal investigator will be responsible for the overall monitoring of the data and safety of study participants, with assistance by members of the study staff, and the Data and Safety Monitoring Board (DSMB), which will be responsible for monitoring the safety of research participants. The DSMB will consist of a neurologist and statistician from another institution who have been approved by the study sponsor (NIA) and by the Wake Forest IRB. Information regarding serious adverse events (SAEs) will be presented to the DSMB every six months, collated in A-B format by an independent statistician. The DSMB may recommend stopping the trial before its planned conclusion if convincing evidence is observed of a treatment difference in adverse events. Recommendations of the DSMB after each review will be presented to the study PI and IRB. Participants will be screened at the beginning of the study and will have their clinical labs and other results (i.e. neuroimaging) monitored carefully at each study visit.

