# Reporting of Unanticipated Problems, Adverse Events or Deviations

Any unanticipated problems, serious and unexpected adverse events, deviations or protocol changes will be promptly reported by the principal investigator or designated member of the research team to the IRB and sponsor or appropriate government agency if appropriate.

All participants will be evaluated for adverse events (AEs) during each study visit. All AEs will be recorded on an adverse event case report form. Based on the nature of the AE, study physicians will determine the severity of the event and the association with the study. All SAEs will be recorded on an IRB "Serious Adverse Event" case report form. SAE are defined as events that are (1) life-threatening or fatal; (2) result in severe or permanent disability; or (3) require hospitalization, other than brief emergent care for non-life threatening conditions. All SAEs will be reported to the IRB within seven calendar days of the investigator or other members of the study team becoming aware of the event. SAEs will be followed until resolution, even if study participation has been terminated.

The "severity" of events will be graded according to the following guidelines:

- 1. *Mild:* The patient is aware of, but can easily tolerate, the event;
- **2.** *Moderate:* The discomfort of the event is severe enough to interfere with some usual activities:
- 3. Severe: The patient is incapacitated, and unable to perform most or all usual activities.

The "study relatedness" will be assigned according to the following guidelines:

- 1. **Definitely Related:** The reaction follows a reasonable temporal sequence and is known to be an effect of the medication or procedure;
- **2. Probably Related:** The reaction follows a reasonable temporal sequence with reasonable suspicion that the study medication or procedure caused or contributed to the event;
- **3. Possibly Related:** The reaction follows a reasonable temporal sequence, and current medical knowledge does not preclude a relationship between the medication or procedure and the event:
- **4. Unlikely:** Current medical knowledge precludes a causal relationship between the medication or procedure and the event;
- **5. Definitely Unrelated:** The cause of the reaction is known to be other than the medication or procedure.

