glucose/ketone levels, and Complete Metabolic Panel (CMP) results will be assessed by a study clinician to determine probable cause. Due to the higher fat/protein content of the MMKD dietary intervention there may be an increased risk for an exacerbation of gout in participants on the diet. Participants will be queried at baseline regarding any history of gout and informed of a potential exacerbation based on the MMKD intervention. Moreover, plasma uric acid levels will be monitored 4 times throughout the study at the screening visit and at weeks 8, 17 and 24. Study participants in the MMKD group may also experience dehydration and constipation. Each will be queried and monitored throughout the study at all interactions. Participants will be encouraged to drink plenty of water and report any significant symptoms to study personnel. MiraLAX may be suggested for participants with persistent constipation. The constraints of the MMKD specifically may lead to an inadequate intake of necessary vitamins and micronutrients. Thus, participants in the MMKD and AHAD groups will each receive the same daily multivitamin supplementation to ensure vital nutrients are consumed, especially in the MMKD group. Participants will be asked not to vigorously exercise during the first week for both interventions and not change their exercise pattern from their habitual pre-study pattern after the first week.

Risks Associated with Head Imaging using MRI: MRI is a non-invasive technique with no known side effects other than possible physical or psychological discomfort. No contrast agent is required. Participants with the following should not participate in MRI studies: metallic implants, such as prostheses, shrapnel, aneurysm clips, or persons with electronic implants, such as cardiac pacemakers. The magnetic field generated by the MRI machine can cause a displacement or malfunctioning of these devices and all participants will be thoroughly screened prior to entering the MRI room. Also, participants who have anxiety or claustrophobia will not be recommended to participate since the head must be placed fully inside the MRI scanner tube. In addition, fatigue and physical discomfort are possible. Earplugs are used in all participants due to the loud noise in the MRI scanning environment. These will not eliminate all sound, so that communication with the participant is still possible.

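### The protocol specifies only serious adverse events for the DSMB's six-monthly by-arm report, but the stated ground for stopping is a treatment difference in adverse events generally

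*Combined protocol and SAP*

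**What the plan says.** Two adjacent sentences under Assessment of Safety, Data and Safety Monitoring, set out what the board receives and what it may do with it.

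- Data supplied: "Information regarding serious adverse events (SAEs) will be presented to the DSMB every six months", in A-B format prepared by an independent statistician.
- Decision allowed: "The DSMB may recommend stopping the trial before its planned conclusion if convincing evidence is observed of a treatment difference in adverse events".

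The section headed Reporting of Unanticipated Problems, Adverse Events or Deviations adds three things.

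- Collection is complete: "All AEs will be recorded on an adverse event case report form". Study physicians then grade severity and relatedness.
- The serious category is narrow: "SAE are defined as events that are (1) life-threatening or fatal; (2) result in severe or permanent disability; or (3) require hospitalization". Short emergency care for conditions that do not threaten life is left out.
- Other reporting takes a different route: "Any unanticipated problems, serious and unexpected adverse events, deviations or protocol changes will be promptly reported". The recipients named are the IRB and the sponsor or a government agency. The board is not among them.

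The same section ends with the events that rule out further participation, among them repeated high fasting glucose and repeated symptomatic hypoglycemia.

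**The concern.** The board's report and its stopping ground cover different sets of events. If the team follows the text, the A-B tables will hold serious events, while the question put to the board concerns adverse events of any grade. An imbalance in non-serious harm, or in safety removals, could build up in one arm without appearing in the report the protocol specifies.

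This matters here for two reasons. Safety and feasibility of the ketogenic diet against the control diet are part of Objective 1. The A-B tabulation is also the only comparison of harms between arms that the visible text describes during the trial; the statistical section names no adverse-event comparison.

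**Working it through.** No figure in the plan is at issue, so the check is a reading of every section that deals with the board, adverse events or expected diet harms.

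**Step 1: which expected harms would normally reach a serious-event table?** Under Potential Risks and Protections Against Risks, the protocol says: "Study participants in the MMKD group may also experience dehydration and constipation". It also names exacerbation of gout, early fatigue and trouble concentrating, possible symptomatic hypoglycemia in the first week, and inadequate vitamin and micronutrient intake. Set against the serious-event definition (threat to life or death, severe or permanent disability, hospitalization):

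| Event named in the protocol | Usually serious by the protocol's definition? |
|---|---|
| Dehydration, constipation | No, unless it leads to hospitalization |
| Gout exacerbation | No, unless it leads to hospitalization |
| Early fatigue, difficulty concentrating | No |
| Symptomatic hypoglycemia | Only if severe enough to meet a criterion |
| Inadequate micronutrient intake | No |
| Removal for fasting glucose above 165 mg/dl at two visits in a row | Not necessarily |
| Removal for symptomatic hypoglycemia on two occasions despite counseling | Not necessarily |

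The right-hand column applies the definition to the usual form of each event. Severe cases could qualify, so the statement is that most would not, rather than that none would.

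**Step 2: does another section send these data to the board by arm?**

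- Reporting of Unanticipated Problems, Adverse Events or Deviations: all events are recorded and graded, but no route to the board is given.
- Data and Safety Monitoring: laboratory and imaging results are watched at study visits. That is review of one participant at a time, with no comparison between arms.
- Safety and Compliance Monitoring: this refers the reader to Protection of Human Subjects for the board's role. The visible text under Ethics/Protection of Human Subjects covers consent, confidentiality and privacy, and does not mention the board.
- Potential Risks and Protections Against Risks: this describes queries, laboratory checks and clinician review of symptoms, all at participant level.

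**Step 3: are the data available?** Yes. Table 2 schedules adverse-event recording at every visit after screening, and clinical or safety laboratory tests at screening and at weeks 8, 17 and 24. Severity and relatedness are already assigned, and an independent statistician already prepares the A-B report.

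**Result.** The data exist and the report exists, but the visible text does not connect them for anything below the serious grade.

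**The case against.** The strongest reply is that the text sets a minimum and forbids nothing. The board is responsible for participant safety and could ask for any table. The cross-reference to Protection of Human Subjects may point to a charter or other document that specifies fuller reports. This stands as a limit: a reader might infer that the board is confined to serious events or is unable to do its job, and the documents do not show that. They show only that serious events are the sole content the protocol specifies.

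A second reply is that the stopping sentence follows the serious-event sentence and may use the broader term as shorthand. On that reading, one added word would make the sentences agree. The reading is possible, but the protocol defines the two terms separately, and the repair would leave most of the named diet harms with no independent comparison by arm.

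A third reply is that harm would not go unnoticed. A reader might infer that a real excess could run to the end of the trial unseen. That is too strong. Physicians assess events at each visit, uric acid is measured four times, significant symptoms prompt clinician review, and individual removal criteria apply. All of this stands, but none of it is a comparison between arms.

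Finally, many of the named harms are expected and mostly mild, and an excess of constipation would not obviously justify stopping. That is fair. Symptomatic hypoglycemia and safety removals are the stronger examples.

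A reader might also want a power figure showing how much more the board would detect. The documents give no adverse-event rates, so any such figure would rest on assumed rates and on the contrasts chosen. Using the full 60 per arm would also overstate what an interim report can show.

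**Conclusion.** The point holds as a mismatch between the data specified for the board and the ground on which it may recommend stopping. It is more than loose wording, because following the section as written leaves out the by-arm data that a judgment on adverse events needs. It should be corrected, but it does not show that participants are unmonitored, and it does not touch the primary analysis.

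The conclusion rests on two assumptions: that no charter or monitoring plan outside these documents already adds the missing tables, and that the named diet harms mostly occur in forms below the serious threshold. If the first is wrong, the remedy shrinks to stating that content in the protocol or citing the document that holds it.

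**What to change.** Amend the reporting sentence in Data and Safety Monitoring so that the six-monthly A-B report contains, for each arm:

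- serious adverse events, as now;
- all adverse events, by severity and relatedness;
- removals under the protocol's existing participation-ending criteria, with the reason;
- symptomatic hypoglycemia;
- shifts in safety-laboratory values.

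Also correct the cross-reference in Safety and Compliance Monitoring so that it leads to the text or charter describing the board's role. If the sponsor in fact intends stopping to be judged on serious events alone, the section should say so plainly, since the two sentences have to be reconciled either way. That alternative would still leave the non-serious harms without a by-arm review during the trial.

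The cost is one amended sentence, one corrected reference and a few more tables in a report already being produced. The downside is slightly more work for the independent statistician. No new data, visits or clinical rules are needed.
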